---

## Change log

Version No.	Effective Date	Reason for the Change / Revision	Supersedes
1	Oct 7, 2016	SAP based on Protocol dated 20 September 2016	None
2	Nov 29, 2017	

• To lower the trigger for imputation based sensitivity analysis for the primary endpoint.

• The Markedly notable analysis tables for laboratory, vital signs and ECG endpoints has been removed.

• More justification for the margin selection has been added in Appendix 5.

• The fluid intake summary was changed to just include information collected in the patient dairy card.

	1 (for the amendment this would be the 1 version)

## 1 Introduction

This document describes the planned statistical analyses for Study 000253 based on protocol Amendment 1, Version 2, dated 25 January 2017.

### 1.1 Definitions/ Abbreviations

#### 1.1.1 Definition of Terms

Terms	Definitions
ITT	Randomized patients
mITT	Randomized patients that have been treated with IMP
Randomised	Subject randomised to trial treatment
Safety set	Patients that have been treated with IMP
Screened	Subject who enters the screening phase

#### 1.1.2 Abbreviations

Abbreviations	Meaning of abbreviations in document
ADR	Adverse Drug Reaction
AE	Adverse Events
AST	Aspartate Aminotransferase
BBPS	Boston Bowel Preparation Score
BHPM	bis-(p-hydroxyphenyl)-pyridyl-2-methane
BMI	Body Mass Index
bpm	Beats per minute
BUN	Blood Urea Nitrogen
CRF	Case Report Form
ECG	Electrocardiogram
FAS	Full-Analysis Set
GGT	Gamma Glutamyl Transferase
IMP	Investigational Medicinal Product
ITT	Intention-to-treat
MedDRA	Medical Dictionary for Regulatory Activities
mmHG	millimeter of mercury
mITT	Modified Intention-to-Treat
NaP/MC	Sodium Picosulfate, Magnesium Oxide and Anhydrous Citric Acid
NI	Non-Inferiority
PK	Pharmacokinetic(s)
PP	Per-Protocol
PT	Preferred Term
SAE	Serious Adverse Event
SD	Standard Deviation
SOC	System Organ Class
WHO	World Health Organization

## 2 Trial Objectives and Endpoints

### 2.1 Objectives

#### Primary Objective

- To demonstrate non-inferiority (NI) of split-dose Sodium Picosulfate, Magnesium Oxide and Anhydrous Citric Acid (NaP/MC) Oral Solution in overall colon cleansing in preparation for colonoscopy compared with split-dose PREPOPIK®

#### Secondary Objectives

- To demonstrate NI of NaP/MC Oral Solution compared with PREPOPIK® in cleansing of the right colon
- To evaluate the cleansing of the transverse and left colon
- To evaluate subjects' tolerability and satisfaction with the bowel preparation
- To evaluate overall safety through the collection of treatment-emergent AEs and clinically significant changes in vital signs, ECGs and laboratory values
- To evaluate pharmacokinetic (PK) characteristics of PREPOPIK® and NaP/MC Oral Solution

### 2.2 Endpoints

#### Primary Endpoint

- Proportion of subjects classified as a responder defined by “excellent” or “good” using the Modified Aronchick scale ([Appendix 3](#) ).

#### Secondary Endpoints

- Proportion of subjects classified as a responder defined by a score  $\geq 2$  in the right segment of the colon using the BBPS ([Appendix 3](#) )
- Proportion of subjects classified as a responder defined by a score  $\geq 2$  in the transverse segment of the colon using the BBPS ([Appendix 3](#) )
- Proportion of subjects classified as a responder defined by a score  $\geq 2$  in the left segment of the colon using the BBPS ([Appendix 3](#) )
- Frequency of each category of the Mayo Clinic Bowel Prep Tolerability Questionnaire ([Appendix 4](#) )
- Incidence and intensity of treatment-emergent AEs and clinically significant changes in vital signs, ECGs, and laboratory values
- Plasma concentration of sodium picosulfate, magnesium and bis-(p-hydroxyphenyl)-pyridyl-2-methane (BHPM)

### 3 Trial design

This is a randomized, assessor-blinded, multi-center study investigating the efficacy, safety, and tolerability of split-dose Sodium Picosulfate, Magnesium Oxide and Anhydrous Citric Acid Oral Solution versus split-dose Low-Volume Sodium Picosulfate, Magnesium Oxide and Anhydrous Citric Acid Powder for Oral Solution (PREPOPIK®) for Colon Cleansing in Preparation for Colonoscopy.

#### 3.1 General Design Considerations

Following appropriate informed consent procedures, subjects who fulfil eligibility criteria and require a colonoscopy will be randomized to one of the two treatment arms.

Only the subject and the site-designated unblinded coordinator and a pharmacist (if applicable) will know the treatment group in which the subject will be participating. The designated unblinded coordinator will instruct the subject on the use of the bowel preparation, and both will sign a nondisclosure affidavit form, preventing the subject and the unblinded coordinator from disclosing the bowel preparation treatment the subject used. Treatment will be blinded to the endoscopist assessing the efficacy of the two tested preparations.

Following randomization, subjects will perform colon cleansing using split-dose NaP/MC Oral Solution or split-dose PREPOPIK®.

NaP/MC Oral Solution (supplied as two 160-mL bottles per subject) needs no further reconstitution before administration.

Subjects randomized to the NaP/MC Oral Solution will begin treatment (first dose) the evening before colonoscopy between 5:00 and 9:00 PM, and will complete treatment (second dose) the following day, at least 5 hours, but no more than 9 hours, prior to the colonoscopy. After drinking the first dose, subjects should drink five (5) or more eight-ounce glasses of clear liquid within five (5) hours. After drinking the second dose, subjects should drink four (4) or more eight-ounce glasses of clear liquid within five (5) hours. Subjects should not ingest anything within two (2) hours before the time of the colonoscopy.

PREPOPIK® (supplied as two sachets per subject) is reconstituted using the cup provided. The doses are prepared by combining the contents of one sachet with approximately five (5) ounces of cold water and stirring for two to three minutes (in some cases the cup may feel warm, which is normal).

Subjects randomized to PREPOPIK® will begin treatment (first dose) the evening before the colonoscopy between 5:00 and 9:00 PM, and will complete treatment (second dose) the following day, at least five (5) hours, but no more than nine (9) hours, prior to the colonoscopy. After drinking the first dose, subjects should drink approximately five (5) eight-ounce glasses of clear liquid within five (5) hours. After drinking the second dose, subjects should drink three (3) eight-

---

[figure not shown]
ounce glasses of clear liquid within five (5) hours. Subjects should stop taking anything by mouth two (2) hours before the time of the colonoscopy.

For a subset of subjects, pharmacokinetic samples will be collected for picosulfate and BHPM concentration. Blood samples will be drawn within 15 minutes before the second dose, and 1 to 2 hours and 3 to 6 hours after the second dose of Prepopik or NaP/MC Oral Solution. Accurate dosing information of both doses and timing of PK samples relative to dosing will be recorded. All study subjects will have a PK sample drawn immediately prior to their colonoscopy.

Subjects will return for three follow-up visits: 24-48 hours (Visit 4), seven days (Visit 5), and four weeks (Visit 6) after the colonoscopy procedure.

### **3.1.1 Trial design diagram**

**Figure 1 Trial Flow Chart**

**Table 1 Trial Assessment Table**

Visit	1 Screening	2 Randomization	3 Procedure	4 Follow-up	5 Follow-up	6 Follow- up (EOT)
Timing versus Procedure	(≤21) Days	(≤10) Days	Colonoscopy (T = 0)	24 – 48 Hours	7 Days (± 2 Days)	4 Weeks (± 2 Days)
Informed consent	x					
Inclusion/exclusion criteria	x	x				
Demographic & Medical History	x					
Body weight, Height 	x	x	x	x	x	x
Urine/Serum Pregnancy Test	x	x				
Schedule colonoscopy	x					
Laboratory (chemistry, coagulation, hematology)	x 		x	x	x	x
PK sampling			x 			
Urinalysis	x		x	x	x	x
ECG	x		x	x	x	x
Physical examination	x		x	x	x	x
Orthostatic vital signs (BP, pulse)	x	x	x	x	x	x
Concomitant medications	x	x	x	x	x	x
Adverse events	x	x	x	x	x	x
Dispense fluid intake diary and study medication		x				
Subject Tolerability Questionnaire			x			
Perform and video-record colonoscopy			x			
Score overall colon preparation – Modified Aronchick scale			x			
Score colon segments preparation – Boston Bowel Preparation Scale			x			
Drug accountability			x			
1. Height will only be collected at screening. 2. Coagulation samples will only be collected at screening. 3. In a subset of subjects, PK samples for sodium picosulfate and BHPM will be taken 15 minutes before the second dose, and 1 to 2 hours and 3 to 6 hours after the second dose of the Sodium Picosulfate, Magnesium Oxide and Anhydrous Citric Acid. 4. All subjects will have a PK sample drawn immediately prior to colonoscopy.						

### 3.2 Determination of Sample Size

The primary objective of this study is to demonstrate NI of NaP/MC Oral Solution to PREPOPIK® for overall colon cleansing prior to colonoscopy using the Modified Aronchick Scale (see [Appendix 3](#) ), as assessed by a blinded endoscopist. A subject is considered to be a “responder” if overall colon cleansing is either “excellent” or “good” on the Modified Aronchick Scale.

The assumed true responder rate for PREPOPIK® is 84% when using the Modified Aronchick Scale (FE2009-01 and FE2009-02). It is assumed that the true responder rate of subjects treated with PREPOPIK® or NaP/MC Oral Solution are the same. A NI margin of 8% was chosen, to ensure no more than a 10% relative decrease from the control. For details on the margin justification please see [Appendix 5](#) . Four hundred and fifty randomized subjects per treatment group are required, in a 1:1 randomization, to maintain at least 90% power to demonstrate the NI of NaP/MC Oral Solution to PREPOPIK® for overall colon cleansing prior to colonoscopy at the one-sided 0.025 significance level.

For PK assessment, on a subset of subjects, blood sample will be collected four times on the day of colonoscopy. Approximately sixty (60) randomized subjects will be included in this PK sub-group. Sixty (60) subjects (approximately 30 per arm) are considered to be sufficient to characterize the population PK for picosulfate and BHPM. In addition to this, all subjects enrolled in the study will have a PK blood sample drawn for BHPM and picosulfate immediately prior to their colonoscopy. The PK assessment on all subjects will be used to explore the potential correlation between AEs and concentration levels of picosulfate, BHPM and magnesium.

#### **4 Subject Disposition**

All subjects screened will be accounted for. All post-randomization discontinuation and reasons for discontinuation will be summarized by treatment group. The number of patients in each patient population will also be summarized by treatment group. Associated listing will also be produced.

The number of subjects screened but not randomized/allocated to treatment will be presented with the reason(s) for screen failure in a data listing.

## 5 Protocol Deviations

Major protocol deviations are a subset of protocol deviations that may significantly impact the completeness, accuracy, and/or reliability of the study data or that may significantly affect a subject's rights, safety, or well-being. A subset of these major protocol deviations will lead to exclusion of the data from the PP analysis set.

Some of the criteria for major protocol deviation are listed below:

- significant deviation in the time of IMP dosing,
- taking the wrong IMP , or
- not following treatment regimen as specified in the protocol.

Regular blinded review of protocol deviations will be conducted prior to data base lock. The rating of protocol deviations as 'minor' or 'major' and exclusion from PP analyses will be also be discussed at these regular meeting and will be completed prior to the declaration of 'clean file' and lock of database.

Major protocol deviations will be summarized by treatment group for the mITT population.

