9.3 Protocol Deviations

Investigators ascertain they will apply due diligence to avoid protocol deviations. Under no circumstances should the investigator contact Ferring or its agents, if any, monitoring the trial to request approval of a protocol deviation, as protocol deviations will not be granted.

Major or minor protocol deviations will be defined and documented prior to database lock. Details will be provided in the Statistical Analysis Plan and/or in the Clean File document.

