9.4.3 Per Protocol (PP) Analysis Set

The PP analysis set comprises all mITT subjects except those excluded as a result of major protocol deviations. Subjects not taking the study medication in the prescribed time intervals will be excluded from the PP analysis set. These subjects will be identified prior to breaking the study blind. The PP analysis set will be analyzed according to the actual randomized treatment received.

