### 6.3 Per Protocol Analysis Set

The Per-protocol (PP) analysis set comprises all mITT subjects except those excluded as a result of major protocol deviations that affect efficacy. These subjects will be identified prior to breaking the study blind.

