### **8.1.2 Treatment Compliance**

The number and proportion of subjects deviating from the treatment regimen will be summarized by treatment group for the safety population. The summary will include the following:

- the number of patient that did not consume the entire dose,
- deviations from protocol mandated administration time,
- the number of patients that did not fast two hours before colonoscopy,
- the number of patient that did not adhere to clear liquid diet 24 hours prior to colonoscopy and
- the number of subject that did not consume the recommended number eight-ounce glasses of clear liquid after each dose of IMP.

Furthermore, associated listing will be produced.

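### Do the different fluid targets after dose 2 leave the per-protocol exclusions undefined, or break the blind in the deviation review?

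*SAP*

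**What the plan says.** SAP 8.1.2 sets out the compliance summary: "The number and proportion of subjects deviating from the treatment regimen will be summarized by treatment group for the safety population". One of its components is "the number of subject that did not consume the recommended number eight-ounce glasses of clear liquid after each dose of IMP". SAP 5 gives some of the criteria for a major deviation, among them "not following treatment regimen as specified in the protocol". It adds that only a subset of major deviations leads to exclusion from the per-protocol (PP) set.

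The rating is done without knowledge of the arm: "Regular blinded review of protocol deviations will be conducted prior to data base lock". Its timing is fixed as well: "exclusion from PP analyses will be also be discussed at these regular meeting and will be completed prior to the declaration of" clean file and the lock of the database.

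On the PP set, Protocol 9.4.3 says "The PP analysis set comprises all mITT subjects except those excluded as a result of major protocol deviations", and the one exclusion it names is dosing outside the prescribed intervals. SAP 6.3 takes all mITT subjects "except those excluded as a result of major protocol deviations that affect efficacy". On the details of major and minor deviations, Protocol 9.3 says "Details will be provided in the Statistical Analysis Plan and/or in the Clean File document".

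The fluid instructions in Protocol 5.1.1 differ by arm. After dose 2 the number of eight-ounce glasses is four or more for NaP/MC and three for PREPOPIK. After dose 1 it is five or more for NaP/MC and approximately five for PREPOPIK.

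**The concern.** Read together, SAP 8.1.2 and SAP 5 bring a fluid shortfall within a criterion that goes to blinded rating. Two things then look open.

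- **Exclusion rule.** No section says whether a shortfall, or how large a shortfall, removes a subject from the PP set.
- **Blind.** A subject who drank exactly three glasses after dose 2 met the target on PREPOPIK and missed it on NaP/MC. A reviewer who sees only the count cannot tell which. A shortfall logged together with a count of three can only belong to NaP/MC.

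At stake would be the PP repeat of the non-inferiority analysis. If exclusions were settled by people who could infer the arm, or under a rule that falls more heavily on the test arm, that analysis would support the primary result less well.

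**Working it through.** **1. Which counts depend on the arm.** Each arm's instruction after dose 2 is applied to whole glasses. PREPOPIK's three is read as a floor, which is an interpretation, but SAP 8.1.2 is concerned with drinking too little.

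| Glasses after dose 2 | NaP/MC (4 or more) | PREPOPIK (3) |
|---|---|---|
| 0, 1, 2 | short | short |
| 3 | short by one | met |
| 4 or more | met | met |

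Only three glasses is classed differently. The amounts are 3 × 8 = 24 oz drunk, against targets of 4 × 8 = 32 oz and 24 oz. After dose 1, four glasses is one short for NaP/MC and has no defined class under PREPOPIK's approximate five.

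**2. Whether the rating needs the arm.** Met or short at three glasses does need it. The review's task is different: it rates deviations as minor or major, and SAP 5 ties major to a possible significant effect on the data or on the subject. Three glasses is zero or one glass short, whichever the arm. A blinded reviewer can decide whether a shortfall of at most one glass is major, and apply that decision to every such subject.

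**3. Who sees the counts.** Under Protocol 7.2.5 the diary holds both fluid intake and dose times. Under Protocol 5.7 the unblinded coordinator enters it in the eCRF, and the sponsor and the blinded endoscopist have no access to it during the trial. SAP 5 also lists taking the wrong IMP, which nobody can identify without the arm. This suggests that staff who know the arm prepare deviations before they reach the review (an inference; no section describes that step).

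**4. Whether the recorded outcome can be affected.** The endoscopist scores cleansing during the colonoscopy (Protocol 6.3). An arm inferred later from a deviation listing cannot alter that score.

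**5. Size.** The plan's own figure is reproduced first. With 84% in both arms, a margin of 8 points, one-sided 0.025 and 90% power:

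n = (1.960 + 1.282)² × 2 × 0.84 × 0.16 / 0.08², which rounds up to 442 per arm. The plan has 450, and power at 450 per arm is 90.5%.

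The documents give no frequency of shortfall, so what follows is illustration.

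- *Subjects at exactly three glasses.* If 1%, 5% or 10% of 450 NaP/MC subjects drank exactly three glasses after dose 2, that is 450 × 0.01 = 4.5, 450 × 0.05 = 22.5 or 450 × 0.10 = 45 subjects.
- *Effect of exclusion.* Let a share f of one arm be excluded, responding d less often than the rest of that arm, with 84% overall. The retained rate r satisfies (1 − f)r + f(r − d) = 0.84, so r = 0.84 + f × d.

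| Share of one arm excluded | Power of the PP analysis (84% in both arms) | Rise in that arm's PP rate, d = 10 to 20 points |
|---|---|---|
| 5% | 89.8% | 0.5 to 1.0 points |
| 10% | 89.0% | 1.0 to 2.0 points |
| 20% | 87.0% | 2.0 to 4.0 points |

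The effect on the mITT analysis is zero, because fluid intake plays no part in membership of that set.

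**The case for a change.** The case for acting is that the question is real and the remedy cheap. Protocol 1.1 describes a washout effect from water retained in the bowel, so reasonable people could disagree on whether low fluid intake affects efficacy, which is the test in SAP 6.3. The higher target after dose 2 belongs to the test arm, so a rule applied correctly could remove more NaP/MC subjects. If those subjects respond less often, the PP difference moves in favor of non-inferiority. A sentence on PP exclusion and a masked met/not-met flag for each dose would settle the matter.

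Part of this stands. The fluid rule is not in either document, the class of three glasses does depend on the arm, and no section describes how diary data reach the blinded review.

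The rest does not carry a change. A reviewer is not forced to learn the arm or leave the case unrated, as step 2 shows. A bare met/not-met flag would make the rating harder, because one glass short would look the same as no fluid at all, and the minor/major decision turns on degree. SAP 5 and Protocol 9.3 expressly place case-by-case rating before lock and allow the detail in the Clean File document, so its absence from the SAP is not an omission from the plan. Any imbalance will also be visible, since SAP 8.1.2 tabulates fluid shortfalls by treatment group and SAP 5 does the same for major deviations.

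**Conclusion.** The observation is accurate, but this is a detail left to the review before lock, not a fault in the plan. No stated rule gives a wrong result. One whole-glass count after dose 2 is classed differently by arm, by a single eight-ounce glass, and its minor or major rating can still be made blind. Non-inferiority and the testing hierarchy rest on the mITT set and are unaffected.

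The effect on the PP sensitivity analysis cannot be estimated from the documents. The illustrated 0.5 to 4.0 points rest on assumed exclusion of 5% to 20% of one arm and an assumed response gap of 10 to 20 points, and they arise only if the review decides that such shortfalls exclude.

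The conclusion assumes that the review settles the point before the blind is broken, as SAP 6.3 requires, and records it in the Clean File document or an equivalent. That document was not available and may already contain the rule.

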## 6 Analysis sets

### 6.1 Intention-To-Treat Analysis Set

The intention-to-treat (ITT) analysis set comprises of all randomized subjects. The ITT analysis set will be analysed according to randomized treatment (as planned).

### 6.2 Modified Intention-to-Treat (mITT) Analysis Set

The primary efficacy analysis will be conducted for the mITT analysis set and is defined as all ITT subjects who received at least one dose of study treatment (i.e., IMP). The mITT analysis set will be analysed according to randomized treatment.

### 6.3 Per Protocol Analysis Set

The Per-protocol (PP) analysis set comprises all mITT subjects except those excluded as a result of major protocol deviations that affect efficacy. These subjects will be identified prior to breaking the study blind.

### 6.4 Safety Analysis Set

The safety analysis set comprises all subjects who took any amount of study medication (i.e., IMP). The safety analysis set will be analyzed according to the actual treatment received.

## 7 Trial population

### 7.1 Demographics and Other Baseline Characteristics

Categorical data will be summarised using numbers and percentages. The percentages are based on the total number of subjects with a corresponding assessment. Continuous data will be presented, for example, using the number of subjects (N), mean and standard deviation, median, minimum and maximum. These analyses will be presented for the mITT and safety population. In addition, since this is a multi-site trial, a summary of demographic characteristics will be presented by trial site. All baseline characteristics will be listed.

#### 7.1.1 Demographics

Descriptive statistics of baseline demographics variables (e.g., age, race and ethnic origin, height, weight and BMI) will be summarized by treatment group.

### 7.2 Medical History

Medical history recorded at screening visit will be coded using Medical Dictionary for Regulatory Activities (MedDRA) version 16.1 or later. Medical history will be listed by treatment and subject, and summarized by treatment group, system organ class (SOC), and preferred term (PT) for the subjects in the mITT and safety analysis sets, separately.

